Participants will be AA adults over the age of 18 who smoked on 4-27 days out of the past 30 at enrollment and have smoked at this non-daily rate for ≥ 3 months. The study will be open to both men and women. We have chosen to focus on AAs only because their unique smoking profile places them at greater risk for tobacco-related disease and death^{44,45,50-52} Importantly, this study represents a starting point for future work that can be expanded to other ethnic groups with high rates of non-daily smoking.

Inclusion Criteria

Inclusion criteria are displayed in the adjoining table. Participants must have smoked 100 cigarettes or little cigars in their lifetime to ensure that

they are smokers and to have smoked at their current rate for ≥ 3 months to avoid enrolling smokers who are in the transitory stages of smoking initiation or reduction/cessation.

Participants also cannot be daily users of other tobacco products, not including e-cigarettes. Other racial groups will be excluded as our primary aim is to evaluate NRT in AA smokers.

Eligibility Criteria

Inclusion Criteria	Exclusion Criteria

 • African American ≥ 18 years of age • Smoke 100 lifetime cigarettes • Smoke cigarettes or little cigars on 4-27 days of the past 30 days • Smoke cigarettes or little cigars at current rate for ≥ 3 months • Use of any tobacco product, not including e-cigs, on 4-27 days in last 30 • Functioning telephone • Interested in quitting smoking • Willing to take NRT for 12 weeks and complete all study procedures 	
 • Unstable cardiac condition (e.g., unstable angina or AMI in the past 4 weeks) • Plans to move from KC during the treatment and follow-up phase • Use of pharmacotherapy, including e-cigs, in the month prior to enrollment • Pregnant or breastfeeding • Another household member enrolled in the study • Unstable housing (e.g., homeless, drug/alcohol treatment center)

Exclusion Criteria

Exclusion criteria are also displayed in the adjoining table. Exclusion criteria are consistent with contraindications for nicotine gum, patch, and lozenge.¹¹

Withdrawal/Termination Criteria

There are no expected circumstances in which the subject’s participation will be terminated by the investigator.

Clarify whether a study subject may participate in another research study while participating in this research study

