
These doses represent a starting point. To enhance the ability of our findings to be translated into practice, counselors will educate participants about the relationship between cpd and NRT dosing and empower them to tailor use to be consistent with their smoking patterns, intensity of withdrawal and craving, and level of side effects. Participants will be taught that, if the NRT dose is adequate, they may still have urges during the day, but most of the time they will not feel strong physical cravings or discomfort. They will also be educated about side effects that may indicate a nicotine overdose (nausea, vomiting, cramps, dizziness) and the need for a dose reduction (i.e., fewer pieces of gum/lozenge per day, reduction from 24 to 16 or 12 hours per day that the patch is worn), as well as symptoms of withdrawal (e.g., irritability, restlessness, anxiety) and strong physical craving that may indicate the need for a dose increase (i.e., more pieces of gum/lozenge per day, increase to longer wear or a higher dose patch). Counselors will probe for smoking level, use of NRT (days used, amount used per day), side effects, symptoms of withdrawal and craving, and general experiences with the

medication during the week 1, 4, 6, 8, and 10 sessions and will provide guidance, as necessary, to ensure that the medication is working optimally for each participant. The PI and study physician will provide oversight on questions and issues that arise related to side effects, dose reductions and/or increases.

Overview of Major Study Events

		Enroll./ Baseline					EOT	Final Follow- Up
		Wk 0*	Wk 1	Wk 4	Wk 8	Wk 10	Wk 12*	Wk 26*
Screening/ Assessments	X	X		X	X		X	X
Intervention								
Counseling		X	X	X	X	X		
Medication Dispensing (C+NRT only)		X (3 to 9- day trial period)	X	X	X		X	

*in person; all other visits are by telephone; EOT=end of treatment

Procedures and Methods

An overview of major study events is provided in the adjoining table.

Initial Screening.

The initial screen will review inclusion/exclusion criteria. Those eligible will be scheduled to complete final eligibility screening within 14 days. All ineligible smokers will be referred to local resources.

Final Screening and Enrollment (Wk 0). Final eligibility screening will be conducted in person and will consist of a pregnancy test on women of childbearing age and obtaining informed consent.

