Counseling Visits (Wks 0,1,4,8,10). Counseling sessions will be completed by phone at Wks 1,4, 8,10, and in person at Wk 0. The number of sessions is consistent with our previous studies where we have achieved visit completion rates of around 80%.^{45,55,56}

NRT Dispensing (Wks 0-1). Participants randomized to C+NRT will be given a trial supply of nicotine gum, patch, and lozenge and be instructed to try each for 3-days. After the 3 to 9-day trial period, they will select and be mailed a 4 week supply of the medication of their choice. They will receive refills of their selected medication at the Weeks 4 and 8 study visits.

Biological Sample Collection (Wk 0,12,26). Urine will be collected three times throughout the study for biochemical verification of cessation at Wk 12 and Wk 26, nicotine intake at Wks 0, 12, 26, and carcinogen exposure at Wks 0, 12, and 26. Additional details regarding each assay are provided in the Measures and Assessment Time Points table.

Retention. We have developed a system of reminders and compensation that have resulted in impressive retention rates in our previous clinical trials. Reminders. One week prior to each scheduled visit a reminder postcard noting the scheduled appointment date and time will be mailed to participants. In addition, participants will be called up to 6 times to remind them of their upcoming visit. A detailed tracking database, with an automated reminder system, will notify counselors of when to send postcards and complete reminder phone calls. Compensation. Participants will be given a \$40 electronically loaded gift card at Wks 0, 12 and a \$20 electronically loaded gift card at Wks 1, 4, 8, 10, 26 in appreciation for their time and participation.

Measures

Our selection of measures (see table) and the measurement time points have been driven by our patient and stakeholder advisory panels.

Measure and Assessment Time Points

Primary Scientific Outcome (Aim 1)

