Side effects. Participants will be asked about symptoms commonly associated with quitting smoking and/or NRT (i.e., difficulty concentrating, irritability, skin rash, mouth/throat irritation, nausea, sleep disturbance, heart burn) Time Points: Wks 4,8,12
Covariates (Aims 1, 2 & 3)
Demographics. Includes gender, age, income, education level, marital status, and use of alcohol Time Point: Wk 0
Smoking history. Includes type of cigarette (menthol, non-menthol), days smoked per month, number of cigarettes smoked per day on days smoked, length of time smoking at current non-daily rate, age of smoking initiation, time to first cigarette of the day (nicotine dependence), use of cigarettes only or cigarettes in combination with alternative forms of tobacco (ATP; e.g., cigars, cigarillos), presence of other smokers in the home, and home smoking restrictions Time Point: Wk 0
Treatment. Includes treatment assignment (C, C+NRT) and, for those randomized to C+NRT, their choice of nicotine gum, lozenge, or patch.

Clearly indicate which procedures, tests, visits, etc., are parts of usual standard therapy and which are performed solely for research purposes.

All tests, procedures, and visits are being performed solely for research purposes and are not billable to insurance companies.

Describe the fate of any body component (blood, CSF, bone marrow, etc.) used in the study, emphasizing confidentiality of labeling of the sample and the sample's destruction or storage.

Samples will be labeled only with a unique study identification number and only members of [name] and [name]'s team will have access to the samples. Samples will be disposed of one month after the final report is sent out to the Principal Investigator, unless participants agree to have their urine stored for future testing.

F. Risk/benefit assessment:

Physical risk

Risks for participating in the study are primarily those related to the use of NRT for participants randomized to the C+NRT arm. The safety of NRT has been demonstrated in hundreds of studies spanning over 30 years of research, including studies of patients who are very low level smokers and nonsmokers. To minimize any possible risk, we will exclude any patients with unstable heart disease (i.e., unstable angina or AMI in the past 4 weeks) per the medical contraindications for NRT.

Nevertheless, NRT, particularly in continuing smokers, can be associated with nausea, jitteriness,

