patients with unstable heart disease (i.e., unstable angina or AMI in the past 4 weeks) per the medical contraindications for NRT. Some participants may experience nausea, jitteriness, insomnia, and vivid dreams. To address these concerns, participants will receive written information and information from their counselor about how to manage any of these symptoms. They will be given advice on when they might need to reduce their nicotine dose (whether through decreasing smoking or decreasing NRT). Discontinuation of NRT may be recommended for participants whose symptoms cannot be otherwise controlled through a dose reduction and/or decreasing smoking. We will track adverse events during regularly scheduled study visits and through spontaneous reports made by participants. [name] and [name] will be made aware of unexpected or serious AEs within 24 hours of the first report by participants; all other AEs will be reviewed weekly by [name] and discussed at regular meetings with [name]. SAEs will be reported to the KUMC HSC and to the FDA with 24 hours of first awareness of the event. Unexpected adverse events that are related to the study medication will be reported to KUMC HSC and to the FDA within 5 working days of first awareness of the event if the event is not serious fatal and within 24 hours of first awareness if the event is serious. Unexpected adverse events that are unrelated to the study medication will be reported to the KUMC HSC during yearly routine event reporting. [name] will determine relatedness for each reported AE. SAEs will be defined as any event experienced by a study subject while on the study medication that is fatal, life-threatening (subject was at risk of death from the event as it occurred), disabling or incapacitating, requires inpatient hospitalization or prolongs a current hospitalization, is a congenital anomaly in the offspring of a subject who received the study medication, or required intervention to prevent permanent impairment or damage.

III. SUBJECT PARTICIPATION

A. Recruitment

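### Pregnancy is excluded and tested at Wk 0, but the visible text attaches no pregnancy-specific check or action to the Wk 4 and Wk 8 NRT refills

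*Combined protocol and SAP*

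**What the plan says.** **Entry.** The eligibility table in II.D lists "Pregnant or breastfeeding" as an exclusion, and the text below it explains the list: "Exclusion criteria are consistent with contraindications for nicotine gum, patch, and lozenge". In II.E, Final Screening and Enrollment (Wk 0), the in-person screen "will consist of a pregnancy test on women of childbearing age and obtaining informed consent". This is the only pregnancy test in the visible text. The Wk 12 and Wk 26 urine samples are for cessation, nicotine and carcinogen assays.

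**Supply.** Under NRT Dispensing in II.E, the first 4-week supply is mailed after a 3 to 9-day trial period. Then: "They will receive refills of their selected medication at the Weeks 4 and 8 study visits". The Wk 4 and Wk 8 contacts are by telephone.

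**What is asked during treatment.** Under NRT dosing in II.E, counselors "probe for smoking level, use of NRT (days used, amount used per day), side effects, symptoms of withdrawal and craving, and general experiences" on the chosen product. The side-effect measure, taken at Wks 4, 8 and 12, covers "difficulty concentrating, irritability, skin rash, mouth/throat irritation, nausea, sleep disturbance, heart burn".

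**Safety text before section III.** "We will track adverse events during regularly scheduled study visits and through spontaneous reports made by participants". NRT discontinuation may be recommended when symptoms cannot be controlled in other ways. A congenital anomaly in a participant's offspring is among the SAE criteria.

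**The concern.** The plan's own entry standard keeps pregnant women off study NRT. The standard is checked once, but product is released again 4 and 8 weeks later. The first mailed supply follows the Wk 0 test closely enough to need no re-check. The two refills do not: by the Wk 8 refill the only test is 8 weeks old.

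A participant who conceives early in treatment is not asked about it in the visible text, and staff who learn of it have no stated step to take about the refill. One existing prompt could also mislead. Counselors teach that nausea and vomiting may mean too much nicotine and call for a lower dose, so a symptom of early pregnancy could be handled as a dosing matter.

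What is at stake is avoidable study-supplied exposure for very few participants, and a decision on NRT that nobody is assigned to make.

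**Working it through.** The plan gives no figure on this point, so there is none to reproduce. The check is a reading of the visible text, then a sizing.

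**1. Entry rule against refill rule**

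| Step | Pregnancy check in visible text | Action if pregnant |
|---|---|---|
| Wk 0 enrolment | Test | Excluded |
| First 4-week supply, after 3 to 9 days | Wk 0 test is recent | Not needed |
| Wk 4 refill, by phone | None specific | None stated |
| Wk 8 refill, by phone | None specific | None stated |

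Pregnancy appears neither among the counselor probes nor among the side-effect items. The stated ground for recommending that NRT stop is uncontrolled symptoms.

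**2. Inputs for size**

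- C+NRT arm: 256 (II.C).
- Share who could become pregnant: 15-35%. Assumed; not in the plan.
- Conceptions per year among them: 3-10%. Assumed; not in the plan.
- Lag from conception to a pregnancy the participant could report: 4 weeks. Assumed.
- Visit completion: about 80%, the rate II.E cites from the group's previous studies.

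**3. Expected number identifiable before a refill**

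With a 4-week lag, only conceptions in Wks 0-4 can be reported by the Wk 8 refill, so the window is 4 of 52 weeks.

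- Low: 256 × 0.15 × 0.03 × 4/52 = 0.089
- High: 256 × 0.35 × 0.10 × 4/52 = 0.689

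**4. Chance of at least one (Poisson)**

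- Low: 1 − exp(−0.089) = 8.5%
- High: 1 − exp(−0.689) = 49.8%

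**5. At 80% visit completion**

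- 0.089 × 0.8 = 0.07, and 1 − exp(−0.07) = 7%
- 0.689 × 0.8 = 0.55, and 1 − exp(−0.55) = 42%

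**6. Which refill matters**

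Conceptions in Wks 0-4 become reportable in Wks 4-8, so nearly all of this count falls to the Wk 8 question. The Wk 4 question would add mainly a conception just before Wk 0 that was too early for the enrolment test. The count above leaves those out.

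**The case against.** **Part of the safety plan is unseen.** The risk section (II.F) points forward to a data safety and monitoring plan, and the safety text available for review starts partway through. Consent pages and counseling scripts are also not reproduced. This objection stands. A reader might infer that the plan has no rule for stopping NRT in pregnancy or for reporting it; the documents support only that none is visible.

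**A pregnancy could surface anyway.** Counselors ask about side effects and general experiences, nausea is asked at Wks 4, 8 and 12, adverse events are tracked at visits and by spontaneous report, and the PI and study physician oversee side-effect and dose questions. This stands against any reading that a pregnancy would go undetected. It does not supply a pregnancy question or an action.

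**The size could be overstated.** A reader might count every conception up to the Wk 8 refill: 256 × 0.35 × 0.10 × 8/52 = 1.378, a 75% chance of at least one. That requires a participant to report a conception on the day it occurs, so it is not a usable upper end.

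**Added harm is not shown.** Participants already smoke, NRT is sold over the counter, and where II.F names a contraindication it is unstable heart disease. Withholding NRT may also mean more smoking. This stands as a reason for a physician's decision rather than automatic stopping. It does not remove the inconsistency, because the trial would be supplying product to someone whom its own criteria exclude.

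**Two extensions are tempting and should not be made.**

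- *Cardiac re-screening.* A reader might want the unstable-cardiac exclusion re-checked too. Such events already fall under adverse-event tracking with 24-hour notice of serious events.
- *The offspring SAE item.* SAEs are limited to the medication period: "SAEs will be defined as any event experienced by a study subject while on the study medication". Assuming 38 weeks from conception to term, a conception in Wks 0-12 means birth at Wks 38-50, which is 12-24 weeks after the last visit at Wk 26. A reader might infer that a refill question would make this item work. It would not, because it adds no follow-up to birth. Nor does the item strictly depend on earlier recording, since spontaneous reports are accepted.

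**Conclusion.** The point holds in a limited form. In the visible text, pregnancy is an exclusion tested only at Wk 0, and the Wk 4 and Wk 8 refills carry no pregnancy-specific check or action. This is a small patient-safety gap and an optional improvement. Sample size, power and the intent-to-treat analysis are untouched.

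The expected size is about 0.1-0.7 pregnancies identifiable before a refill in the whole trial, an 8-50% chance of at least one, falling to about 7-42% at 80% visit completion. These figures rest on the assumed shares and the assumed 4-week lag. They count pregnancies that could be identified, not harms. Confidence is moderate because part of the safety text was not available.

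**What to change.** On the existing Wk 4 and Wk 8 calls in the C+NRT arm, ask whether the participant is or may be pregnant before releasing the refill. If only one call can carry the question, use Wk 8.

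If the answer is yes:

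- hold the refill for a prompt study-physician decision that weighs NRT against continued smoking;
- record the pregnancy with the roles that already receive serious-event notices;
- keep the participant in follow-up and in the intent-to-treat analysis.

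State this in NRT Dispensing (II.E) and in the discontinuation text before section III.

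**Cost.** One question on two calls already scheduled at 15 minutes, reusing a criterion that the screening questionnaire must cover (III.B), plus two or three sentences. No new visit, test or staff. The downside is a short refill delay, with possible extra smoking meanwhile, for the few who answer yes.

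The sponsor should first check the safety text that was not available here. If it already contains such a rule, nothing needs to change.

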Specific Aim 1: To compare abstinence rates among AA non-daily smokers receiving either smoking cessation counseling (C) or smoking cessation counseling in combination with NRT (C+NRT). Hypothesis: Participants randomized to C+NRT will have significantly higher biochemically verified smoking abstinence than participants randomized to C at 12 weeks end of treatment (primary outcome) and at 26 week follow-up. Analytic strategy: The chi-square test will be used to compare the verified abstinence rates at Week 12 (primary cessation endpoint) and Week 26 (secondary cessation endpoint) between C and C+NRT. For our primary comparison, those lost to follow-up will be considered as smokers. Assuming the expected treatment effect, we will descriptively examine the cessation rate within the C+NRT group by choice of NRT. A statistical comparison will not be conducted as we do not know a priori who will choose what and the choice will not be random. We also will look at completers only and will utilize multiple imputation techniques to ensure valid comparisons between the two groups if the loss to follow-up is not random. Secondly, we will utilize Generalize Estimating Equation methodology to longitudinally compare verified abstinence. We will then examine the effects

of the covariates and patient and provider outcomes listed in the measurement table above on this endpoint by utilizing best subsets selection techniques. Our goal is to identify a final model utilizing the smallest subset of covariates that describes cessation over the length of the study. Given the sample size and expected cessation rate, we anticipate a model that contains at most six covariates. We expect no difference in the distribution of demographic and smoking history covariates between groups and we will not statistically compare those as per CONSORT recommendations for randomized clinical trials. Within the NRT treatment group, we will examine the effect of NRT adherence over the first 12 weeks on verified cessation using logistic regression.

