Smoking abstinence at Wk 12 (primary cessation outcome) and Wk 26 (secondary cessation outcome). Biochemically confirmed at Wk 12 using urine anabasine and anatabine, with the recommended cut-off of 2 ng/ml to differentiate smokers from non-smokers. ⁵⁰ These tobacco alkaloids are considered the gold standard for confirming abstinence when cotinine measurements are not valid – i.e., detectable levels of cotinine could reflect NRT use or smoking. ⁵⁰ Biochemically confirmed at Wk 26 using urinary cotinine, the proximate metabolite of nicotine, with the recommended cut-off of 50 ng/ml used to differentiate smokers from non-smokers. ⁵¹ Time Points: Wk 12, 26
Secondary Patient- and Provider-Derived Outcomes (Aim 2)
Nicotine intake (total nicotine equivalents/creatinine). Assessed by urine; quantified by examining the sum of four of the major nicotine metabolites (cotinine + cotinine-glucuronide + trans-3'-hydroxycotinine + 3HC-glucuronide) to creatinine ratio using procedures described by [name] (consultant). ⁵¹ Total nicotine equivalents/creatinine represents the current gold standard for estimating nicotine intake/exposure from tobacco. ⁵⁷ To ensure that nicotine metabolites detected at Wk 12 are a result of tobacco exposure and not NRT use, we will schedule the urine collection for 7 days after the last dose of NRT. This 7-day time frame is more than adequate given the 15-20 hour (3-4 day) elimination half-life of cotinine and accounts for the substantial individual variability in the rate of elimination of nicotine. ⁵⁸ Time Points: Wks 0,12,26
Carcinogen exposure [NNAL, PAH]. Assessed by urine; quantified by examining NNAL (4-(methylnitrosamino)-1-(3)pyridyl-1-butanol) and polycyclic aromatic hydrocarbons (PAH) and specifically, 1-hydroxypyrene (1-HOP), using procedures described by [name] (consultant). ⁴⁰ While there are >70 established carcinogens in tobacco, NNAL and PAH are widely considered to be among the most important causative agents in the development of lung and esophageal cancer ^{38,39,59} and reflect the current gold standard for estimating carcinogen exposure from tobacco products. Time Points: Wks 0,12,26
Days Abstinent. Cumulative number of days abstinent Time Points: Wks 1,4,8,10,12
NRT adherence. 3-day recall of NRT use (C+NRT only) -- i.e., pieces of gum, lozenge, or number of patches used in the last 3 Time Points: Wks 4,8,12

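### Week 26 abstinence is verified by cotinine alone, with nicotine-product use at that visit neither barred nor recorded; a cheap improvement to a secondary endpoint

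*Combined protocol and SAP*

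**What the plan says.** The Measure and Assessment Time Points table (section II.E) verifies the same construct with a different marker at each visit.

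- Week 12, primary: "Biochemically confirmed at Wk 12 using urine anabasine and anatabine, with the recommended cut-off of 2 ng/ml".
- Week 26, secondary: "Biochemically confirmed at Wk 26 using urinary cotinine, the proximate metabolite of nicotine, with the recommended cut-off of 50 ng/ml".

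The table's reason for the Week 12 choice is that "detectable levels of cotinine could reflect NRT use or smoking". The Laboratory Tests paragraph of II.E repeats both rules. No fallback marker is given for Week 26.

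Both results are analysed under Specific Aim 1 (II.C): "The chi-square test will be used to compare the verified abstinence rates at Week 12 (primary cessation endpoint) and Week 26 (secondary cessation endpoint". The next step is a longitudinal model: "Secondly, we will utilize Generalize Estimating Equation methodology to longitudinally compare verified abstinence". Weeks 12 and 26 are the only visits with verified abstinence.

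On nicotine products:

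- For the Week 12 nicotine-intake measure the table says "we will schedule the urine collection for 7 days after the last dose of NRT". No such interval is given for Week 26.
- Adherence is a "3-day recall of NRT use (C+NRT only"), at Weeks 4, 8 and 12.
- The exclusion for pharmacotherapy and e-cigarettes (II.D) covers only the month before enrollment. The only restriction during participation is on joining another cessation study.
- Study NRT is a 12-week supply, and over-the-counter availability was one reason for choosing these products (II.E, NRT).

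**The concern.** Cotinine shows nicotine exposure, whatever the source. By the protocol's own account it cannot tell a person who smokes from one who has quit and uses NRT. Applied as written at Week 26, the 50 ng/ml rule would not count as abstinent someone who has stopped smoking but is using gum, a lozenge, a patch or a nicotine e-cigarette around the visit.

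Three things depend on this: the Week 26 hypothesis in Aim 1, its chi-square test, and the longitudinal model. Because the marker changes completely between the two verified visits, some of any apparent change over time may come from the marker. And because nicotine-product use is not recorded at Week 26 in either arm, the sponsor could not show afterwards that the problem was small.

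**Working it through.** **1. Reproduce the plan's power (II.C).** Inputs: 128 in C, 256 in C+NRT, control rate 10%, type 1 error 5% (taken as two-sided). The uncorrected chi-square approximation is

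power = Φ[(p2 − p1 − 1.96·SE0)/SE1], with SE0 = √[p̄(1 − p̄)(1/128 + 1/256)] and SE1 = √[p1(1 − p1)/128 + p2(1 − p2)/256].

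For 10% against 20%: p̄ = (12.8 + 51.2)/384 = 0.1667, SE0 = 0.0403, SE1 = 0.0364, so Φ[(0.10 − 0.0791)/0.0364] = Φ(0.574) = 71.7%. For 22.5% and 25% the results are 87.6% and 95.7%. The plan states 71%, 87% and 95%, so its figures reproduce. Exact binomial enumeration of the same test gives 73%, 88% and 96%; exact values are used below.

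**2. Would light nicotine use fail the 50 ng/ml rule?** Inputs: 807.8 ng/mg cotinine in AA non-daily smokers (I.B table), matched in II.E to 5.5 mg of nicotine a day; 1 mg absorbed per 2 mg gum or lozenge (II.E). Then 807.8/5.5 ≈ 147 ng/mg per mg absorbed. At an assumed urine creatinine of 1 mg/ml, one piece a day gives about 147 ng/ml; at 0.5 mg/ml, about 73 ng/ml. Both exceed 50.

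**3. Would study NRT that stopped at Week 12 matter?** No. At the upper half-life the table gives, 20 hours, the fraction left after 7 days (168 hours) is 2^(−168/20) = 0.3%, and after 14 weeks essentially nothing. Only use around Week 26 counts.

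**4. Effect on the Week 26 test.** Let f and g be the shares of true abstainers in C+NRT and C who fail cotinine because of nicotine products. The observed rates are p2(1 − f) and p1(1 − g). The documents give neither share, so the range is assumed, and the Week 12 planning rates of 10% and 20% are assumed to hold at Week 26.

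| f (C+NRT) | g (C) | Observed C | Observed C+NRT | Difference (points) | Exact power |
|---|---|---|---|---|---|
| 0 | 0 | 10% | 20% | 10 | 73% |
| 10% | 10% | 9% | 18% | 9 | 67% |
| 20% | 20% | 8% | 16% | 8 | 61% |
| 10% | 0 | 10% | 18% | 8 | 55% |
| 20% | 0 | 10% | 16% | 6 | 36% |
| 0 | 10% | 9% | 20% | 11 | 82% |

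At the upper planning rate of 25%, f = 10% with g = 0 gives 10% against 22.5% and power of 88%, compared with 96% without misclassification.

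**5. Effect on the GEE.** If true abstinence in C+NRT stays at 20% and f = 10%, the data show 20% at Week 12 and 18% at Week 26: an apparent relapse of 2 points produced by the marker. With equal shares the risk ratio stays at 2.0 (18/9), and the odds ratio barely moves: (0.20/0.80)/(0.10/0.90) = 2.25 becomes (0.18/0.82)/(0.09/0.91) = 2.22.

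**The case against.** Cotinine at Week 26 is a reasoned choice. The visit falls about 14 weeks after the 12-week supply nominally ends, the Week 10 counseling session covers ending medication, and step 3 shows that no residue of study NRT would remain. A reader might infer that the protocol contradicts itself. It does not: it matches the marker to the exposure it expects at each visit. What stands is that nothing checks that expectation. One related point also needs reconciling: the events table appears to mark medication dispensing at Week 12, whereas the NRT Dispensing paragraph gives refills only at Weeks 4 and 8. This bears on when study NRT ends.

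A reader might infer that the bias runs against C+NRT because that arm may hold leftover product. The documents neither mention nor quantify leftover product, and C participants have the same over-the-counter access. The last table row shows that bias can also favour C+NRT.

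A reader might infer that changing assays undermines the arm comparison in the GEE. At each visit both arms have the same assay, so the change is aliased with time, not with treatment. The arm contrast on the ratio scale is materially distorted only if nicotine use differs by arm, and the Aim 1 hypotheses compare arms and not change over time.

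Finally, coding these participants as smokers follows from applying the cut-off. The plan has no explicit rule for reported abstinence with positive cotinine. II.C also makes no power claim for Week 26, so no stated figure is contradicted.

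**Conclusion.** The point holds as a cheap improvement to a secondary endpoint and a supporting model. The primary test and the sample size are untouched. As written, the Week 26 rule cannot distinguish a nicotine-using abstainer from a smoker, and the trial collects nothing that would identify one.

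The size is unknown. Under the assumed shares and carried-over planning rates, power for 10% against 20% moves from 73% to anywhere between 36% and 82%; equal use in both arms gives the moderate losses, to 67% or 61%. The direction depends on which arm's abstainers use more nicotine products. The GEE time effect should not be interpreted as relapse while the marker changes with visit.

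**What to change.** 1. Ask both arms about NRT and e-cigarette use in the past 7 days at Weeks 12 and 26.
2. Run anabasine/anatabine (2 ng/ml) on the Week 26 urine of self-reported abstainers, and use that single rule at both visits for the Week 26 test and the GEE. Keep the 50 ng/ml cotinine definition as a prespecified sensitivity analysis.
3. If only self-reported abstainers with cotinine of 50 ng/ml or more are retested, state that the Week 26 rule (cotinine below 50, or alkaloids below 2) still differs from Week 12, and do not interpret the GEE time effect as relapse.

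The cost is one survey item and extra runs of an assay the trial already uses, on urine it already collects. The number of runs depends on how many report abstinence. At the planning rates with full follow-up, true abstainers alone would number about 64 (12.8 + 51.2) to 77 (12.8 + 64), plus any false reports. This should be decided early: samples are discarded one month after the final report unless the participant agrees to storage (II.E and IV.B).
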